The main analyses will follow the principle of intent-to-treat, and include all 480 food insecure caregivers in the study arm to which they were allocated. We aim to minimize missing data by employing interviewer-administered surveys and communicating to participants the protections of a certificate of confidentiality. Using these strategies, item non-response ranged from 0-3% in our CRx trial. To avoid potential bias due to missing data, analyses will be conducted using multiple imputation with the chained equations method or inverse probability weighting to account for dropout and/or item non-response. In addition, characteristics of caregivers who complete each interview will be compared to caregivers who do not.

To fully leverage the longitudinal data, generalized linear mixed-effects models (GLMM) will be fit with particular interest in the time (baseline and 7, 30, 90 and 180 days and 12 months post-discharge) by study arm interaction. Based on this model, appropriate contrasts to test the intervention effect at specific time points (e.g., 12 months) will be constructed. These contrasts will permit examination of early versus late effects of the intervention, valuable information for future iterations of this and other parent/caregiver self- and family management interventions. GLMM can be used for continuous (e.g., food security score, amount of fruits and vegetables per day), ordinal (e.g., caregiver self-efficacy, food insecurity categories), or binary (e.g., enrollment in SNAP/WIC) outcomes. If there is a serious imbalance in baseline covariates despite randomization, those covariates will be included in the model. Latent growth curve modeling is a viable alternative to GLMM and will be explored when sufficient variability in the distributions of patterns of outcomes by time points exist (e.g., with the binary outcomes there will be a limited number of potential patterns).

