We will also use survival analysis methods and methods for analyzing count data (e.g., Poisson or negative binomial regression) to assess the following secondary outcomes among children: 1) time to child follow-up for the post-discharge medical visit, 2) time to and number of ER visits, 3) time to and total days of hospitalization. For example, time from discharge to first ER visit will be calculated for each subject and those who never have an ER visit will be censored at the end of study follow-up. Stratified Cox proportional hazards regression models will be fit with intervention group as the independent variable and discharge location (e.g. transplant unit, general unit) as a stratification factor, due to the potential for different underlying rates based on discharge location. The proportional hazards assumption will be checked using log-log plots of survival and Schoenfeld residuals.

For the primary outcome (self-efficacy for self-care at 12 months) a sample of 236 caregivers per arm allows for detection of an intervention group difference of similar magnitude as that found in our CRx trial (3.56 +/- 1.47 vs. 3.92 +/- 1.24). Calculations were performed under the following conditions: with nonparametric adjustment accounting for the fact that an ordinal logistic model with intervention group as the only covariate is equivalent to a Mann-Whitney U test; sample size calculation using a group allocation of 1:1; power=0.8; $\alpha=0.05$. We will therefore enroll 480 food insecure caregivers to accomplish Aim 1. With this sample size, power is sufficient to see at least a 0.26 standard deviation (SD) difference in Generalized Self-Efficacy between intervention and control groups. Assuming a standard deviation of about 5 (based on US adult population norms), a 0.26 SD difference would be equal to 1.3 points.

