We will use the analytic approach described for Aim 1, following the principles of intent-to-treat. Here, we discuss analytic issues unique to Aim 2. To facilitate ease of interpretation of the primary outcome, we will linearly rescale the composite score for the Child HCAHPS dimension of satisfaction with discharge.⁵⁹ Three possible responses for each of the five items included in this dimension will be scored as: No=1; Yes, somewhat=2; Yes, definitely=3. Scores will be transformed using the formula: $y = 100 * (x-a)/(b-a)$ where y=the transformed score, x=the original score, a=the minimum possible score and b=the maximum possible score. Transformed items will be averaged to generate the composite score (range 0-100, higher values mean greater satisfaction). Of particular interest for the non-inferiority hypothesis (H2a) will be the confidence interval for the difference (usual care - CRx-H) and whether or not the upper limit of the confidence interval exceeds the non-inferiority margin. Of note, superiority of the intervention with respect to satisfaction with care, child and caregiver health, and stigma will also be tested as this can be done without penalty. Caregiver satisfaction will be measured at 7 days post discharge and will reference the index hospitalization; no longitudinal analyses will be conducted for this outcome. Typically, analyses of HCAHPS data adjust for case-mix (age, education and general health status); this will be feasible, but given the randomized design and single-site analysis, adjustment should not necessary. To determine whether there are substantial differences in the intervention's effect on food insecure compared to food secure caregivers, the intervention by food security status interaction will be tested. As in Aim 1, we will examine for differential intervention effects on primary and secondary outcomes among racial and ethnic groups, and by sex, using effect modification analyses. Some analyses will be restricted to the food secure group (N=160) to provide a more complete assessment of the impact of the intervention on this group (e.g., changes in knowledge and attitudes about food insecurity and changes in food security over time).

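### Baseline covariates enter the main models only after a serious imbalance is seen; a short fixed set of prognostic covariates would recover precision at almost no cost

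*SAP*

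**What the plan says.** The SAP (Aim 1, Analysis and Sample Size Justification) fits generalized linear mixed models with time, arm and their interaction. Its only rule on covariates is: "If there is a serious imbalance in baseline covariates despite randomization, those covariates will be included in the model". It gives no threshold, no test and no list of candidates.

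The Aim 1 sample size assumes no adjustment. It relies on the fact that "an ordinal logistic model with intervention group as the only covariate is equivalent to a Mann-Whitney U test".

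The Aim 2 analysis section adopts the Aim 1 approach. It notes that the usual case-mix factors for the satisfaction survey (age, education, general health) could be used, but concludes that "given the randomized design and single-site analysis, adjustment should not necessary".

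Nothing else fixes a covariate set for either primary comparison. The full-trial protocol's Statistical Plan names no covariates. Discharge location is a stratification factor only in the Cox models for secondary outcomes. The moderator terms address effect modification. Baseline self-efficacy appears in the mixed model as a time point of the response, not as an adjustment covariate.

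**The concern.** Randomization makes the unadjusted comparison valid. The reason to adjust is that a covariate which predicts the outcome removes residual variance, and that gain depends on prognostic strength, not on how the covariate happened to fall between arms. A rule driven by imbalance leaves out a strong predictor that is moderately imbalanced and admits a weak predictor that is badly imbalanced. It also leaves the primary model unsettled until someone has looked at baseline data by arm and judged what counts as serious.

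At stake is mainly precision from data the trial already collects. Aim 1 has little slack: the calculation needs 236 per arm and 480 are enrolled (240 per arm). In Aim 2 a narrower interval would help directly against a 1.6-point non-inferiority margin. The Aim 2 reason for not adjusting speaks to bias and leaves precision unanswered.

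**Working it through.** **1. The plan's own figure.** Inputs, all from the SAP's Aim 1 sample size paragraph: means and SDs "3.56 +/- 1.47 vs. 3.92 +/- 1.24", 1:1 allocation, power 0.80, alpha 0.05. The number of sides is not stated.

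- Difference = 3.92 − 3.56 = 0.36
- SD = √[(1.47² + 1.24²)/2] = 1.360, so d = 0.36/1.360 = 0.265
- n per arm = 2(1.960 + 0.842)²/d² = 224, or 225 with the t distribution
- Mann-Whitney adjustment: multiply by π/3, giving 235 (normal) or 235.6, i.e. 236 (t)

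This reproduces the SAP's "a sample of 236 caregivers per arm allows for detection of an intervention group difference". A one-sided test would give 185 after the same adjustment, so the calculation is two-sided. The stated 80% power is therefore correct for an unadjusted analysis.

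**2. What always adjusting would give.** The documents give no covariate-outcome correlation, so I take R² (the share of outcome variance explained) as 4%, 10%, 20% and 30%. I use a linear approximation to the 5-point outcome, one covariate, a between-arm contrast at 12 months, and exactly 80% unadjusted power (standardized effect 1.960 + 0.842 = 2.802).

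Power if always adjusted = Φ(2.802/√(1 − R²) − 1.960). At R² = 10%: 2.802/0.949 − 1.960 = 0.993, so power is 84.0%.

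**3. What the rule gives.** A trigger has to be assumed; I take a baseline difference at p<0.05. Let w be the standardized baseline difference between arms, and θ the standardized effect (2.802, or 0 under the null).

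- If |w| < 1.96 the unadjusted statistic is used. Given w, it is normal with mean θ + w√R² and variance 1 − R².
- Otherwise the adjusted statistic is used. It is normal with mean θ/√(1 − R²) and variance 1, independent of w.

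Integrating over w gives:

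| R² (assumed) | Power, rule | Power, always adjusted | Overall type I error, rule | Type I error, imbalance just below trigger |
|---|---|---|---|---|
| 4% | 80.2% | 81.6% | 4.9% | 5.7% |
| 10% | 80.5% | 84.0% | 4.7% | 6.7% |
| 20% | 80.9% | 87.9% | 4.5% | 8.2% |
| 30% | 81.3% | 91.8% | 4.2% | 9.7% |

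The last column covers |w| from 1.30 to 1.96, which is 2[Φ(1.96) − Φ(1.30)] = 2(0.975 − 0.903) = 14% of trials. Simulation at 240 per arm agrees: 6.9%, 7.9% and 10.0% at R² of 10%, 20% and 30%.

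**4. In terms of sample size.** Always adjusting matches the stated power with 236 × (1 − R²) per arm: 227, 212, 189 and 165.

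**5. Aim 2.** On the same linear approximation, adjustment multiplies the interval's half-width by √(1 − R²): 0.98, 0.95, 0.89 and 0.84. R² for the satisfaction score is likewise an assumption.

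**6. If the contrast is change from baseline.** The SAP's interest in the time-by-arm interaction also allows the 12-month effect to be tested as change from baseline. On the linear scale, a covariate with the same effect at every visit then cancels. Adjusting for it adds no power, and its imbalance does no harm. Simulation (240 per arm, visit correlation 0.5 assumed, same 14% slice) gives a conditional type I error of 4.4%, 4.7% and 4.9% at R² of 10%, 20% and 30%.

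**The case against.** The strongest reply is that the unadjusted analysis is valid and adequately powered on the plan's own terms, so a fixed list is good practice and nothing more. The validity part stands, and so do several limits.

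- **General inflation of the error rate.** A reader might infer this. The documents do not support it: applied mechanically, the rule is slightly conservative overall (4.2% to 4.9%). The excess just below the trigger is offset elsewhere and arises only for the between-arm contrast. Real inflation would need someone to choose the most favourable of the unadjusted, triggered and fully adjusted results (6.3% to 7.5% in simulation, covariate-outcome correlation 0.3 to 0.5, one to five covariates). The undefined word leaves room for that, but the SAP does not propose it.
- **A chance-dependent odds ratio.** A reader might infer that adding covariates changes the odds ratio being estimated. That applies to ordinary logistic regression. In a mixed model with a subject random intercept, most of the shift is absorbed: a check with a true log odds ratio of 0.50 and a strong covariate gave 0.498 unadjusted and 0.496 adjusted. The SAP does not detail its random effects, but this is not a ground for the point.
- **Loss in every trial.** This is too strong. When the trigger fires on a useful covariate the model does adjust, and under a change-from-baseline contrast there may be nothing to lose.
- **Assumed inputs.** The trigger, R² and single covariate are not in the documents. At R² = 4% the loss is only about 1 point.
- **Aim 2.** No imbalance trigger is stated specifically for satisfaction. The section takes over the Aim 1 approach by reference and expresses a preference against case-mix adjustment. That is defensible on bias; it does not address precision.

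What remains is a stated rule that selects covariates on the wrong criterion, for which a better rule costs very little.

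**Conclusion.** The point holds as a cheap improvement in precision and prespecification, not as an error that invalidates the analysis. For a between-arm contrast at 12 months, the rule forgoes about 1, 4, 7 and 10 points of power at R² of 4%, 10%, 20% and 30%, relative to always adjusting. The stated power and overall type I error are sound. Conditional type I error reaches about 7% to 10% (R² 10% to 30%) in the roughly 14% of trials just below a p<0.05 trigger, and only for that contrast. If the effect is tested as change from baseline, a covariate with a constant effect over time brings neither the gain nor the conditional error. Under either contrast, the covariate set is still decided after looking at the arms.

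**What to change.** Delete the imbalance trigger. In its place, name a short fixed set of prognostic covariates and include it whatever the balance, in both the Aim 1 primary model and the Aim 2 satisfaction interval. A reasonable set is the food security score at screening, caregiver age, education and general health, and the child's unit at enrolment. Report the unadjusted result as a sensitivity analysis. State whether the 12-month contrast is between arms or change from baseline, since the gain depends on it.

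Use only values measured before randomization, or values that allocation cannot affect. This needs one reconciliation. The SAP (Aim 1, strategy and methods) places the baseline survey after randomization, while the full-trial protocol (B1, Introduction) places randomization after the baseline survey. The food security score comes from screening, so it is unaffected, but education and general health are survey items, and general health in particular needs the order settled.

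The cost is SAP wording, that reconciliation and a few degrees of freedom. No new data are needed.

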CommunityRx-Hunger (CRx-H) Overall Statistical Analysis Plan (SAP)

NCT04171999

March 2, 2018

CommunityRx-Hunger RCT Statistical Design and Power

NIH funding will support a double-blind randomized controlled trial (N=640, 480 food insecure, 160 food secure) and qualitative research to evaluate the impact of CRx-H on adult and child outcomes. This research will fill important gaps in knowledge about how best to intervene in a hospital setting to support food insecure parents or caregivers with a hospitalized child. The study design and analytic plan incorporate best practices to ensure a robust and unbiased approach, drawing on the mixed methods and large scale clinical trials expertise of the multidisciplinary team. The CRx-H trial will be registered on clinicaltrials.gov in accordance with NIH policy. All reporting will comply with CONSORT guidelines. For each aim, we provide hypotheses.

Aim 1: Screening-based interventions target the highest-risk individuals in a population. Food insecurity screening recommended for use in the healthcare setting classifies people dichotomously as food insecure or not. But food insecurity is a dynamic and complex condition and we have found that a child's hospitalization is a triggering event for 19% of previously food secure caregivers. Healthcare systems are moving quickly to adopt a screening-based approach to intervening on food insecurity and other HRSNs, but little is known about what impact this new practice will have on food insecure people. The purpose of Aim 1 is to study the effect of a screening-based approach to delivery of the CRx-H intervention on caregiver self-efficacy and more distal caregiver and child health and healthcare outcomes.

Among caregivers of hospitalized children who screen positive for household food insecurity we will evaluate the longitudinal effects of CRx-H versus usual care on self-efficacy (primary outcome), severity of caregiver and child food insecurity, adult and child nutrition and health, and child healthcare utilization (secondary outcomes).

Hypothesis 1a. The intervention group will report higher levels of self-efficacy at 12 months compared to controls.

Hypothesis 1b. Adults in the intervention group and their children will have a higher rate of food security and nutritious intake at 12 months compared to controls and their children.

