Hypothesis 1c. Children of caregivers in the intervention group will present sooner for the post-discharge follow-up visit and will have a longer interval to ER visit or hospitalization than children of control group caregivers.

RCT Strategy, Timeline, Methods, and Key Measures: After pretesting with 10 food secure and 10 food insecure caregivers, a consecutive sample of 640 caregivers of hospitalized children at Comer Children's Hospital (CCH) will be enrolled in the RCT Y1-Y3. Eligible subjects will include caregivers who are English-speaking (~95% of CCH caregivers), who live in the 16 ZIP code target region and who self-identify as a primary caregiver of a child <18 years old hospitalized in CCH's general, intensive care or transplant units. Caregivers of well newborns will be excluded as will caregivers of children expected to be hospitalized for <24 hours and >30 days (~25% and 7% of caregivers, respectively, meeting above criteria). To be eligible, caregivers must agree to receive text messages from the research team.

CCH will admit ~10K unique children during the 24 month enrollment period. Based on CCH admission data and our preliminary studies, at least 3400 caregivers of these children will meet all eligibility criteria. New admissions will be identified via the EMR by HIPAA-trained research staff. Caregivers will be consecutively approached, screened for eligibility and enrolled on the child's hospital unit within 72 hours of the child's admission. This recruitment protocol uses the same successful strategy we implemented for prior studies, including a cross-sectional study of food security in caregivers of children hospitalized at CCH (85% cooperation rate) and the CRx trial (80% completed the 1 and 3 month surveys, 71% cooperation with all 3 follow-up surveys). For the CRx trial, we approached 3034 adults and successfully screened 70% (18% refused, 12% could not be screened due to feeling unwell, sleeping or they were called to their appointment). Given the expected number of eligible caregivers (3400), a projected 70% screening rate, and a 43% food insecurity rate, we project that we will need less than 24 months to enroll the target sample of 480 food insecure and 160 food secure + 20 pretest participants (3400 eligible/24 months x 70% screened x 43% food insecure = 1023 food insecure eligible and 1357 food secure eligible caregivers).

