The proposed sample size of 640 is sufficient based on a non-inferiority margin of 1.6 points in patient satisfaction (primary outcome), assuming group allocation 1:1, power=0.8, $\alpha=0.05$, standard deviation=8 (10% of the mean in a prior study of Adult HCAHPS). The non-inferiority margin of 1.6 points is less than the difference in this domain identified between non-Hispanic white and non-Hispanic Black adults reporting satisfaction with discharge (79.3 vs 77.4). For the analysis of changes in food security status during follow-up among the food secure group, 80 caregivers per study arm will provide 80% power ($\alpha=0.05$) to detect a 0.45 standard deviation difference in the food security score at a given time point.

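### The 80% power for 12-month self-efficacy (Aim 1 primary outcome) assumes almost no loss to follow-up: 236 per arm are needed with data and 240 are enrolled

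*SAP*

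**What the plan says.** The SAP's Aim 1 hypothesis fixes the time point: "The intervention group will report higher levels of self-efficacy at 12 months compared to controls". The sample size paragraph of Aim 1 (Analysis and Sample Size Justification) says "a sample of 236 caregivers per arm allows for detection of an intervention group difference of similar magnitude" to the prior CRx result, 3.56 (SD 1.47) against 3.92 (SD 1.24). The listed conditions are 1:1 allocation, power 0.8, alpha 0.05 and a nonparametric adjustment, justified on the ground that "an ordinal logistic model with intervention group as the only covariate is equivalent to a Mann-Whitney U test". Dropout is not among them. The paragraph continues: "We will therefore enroll 480 food insecure caregivers to accomplish Aim 1". That is 240 per arm. Under the randomisation plan a stratum closes when its accrual goal is met, so no surplus is planned.

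The only follow-up rates in the documents are those of the prior CRx trial, in the Aim 1 section on strategy and methods: "80% completed the 1 and 3 month surveys, 71% cooperation with all 3 follow-up surveys". No expected 12-month retention is given for this trial.

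For analysis, the SAP plans intent-to-treat on all 480, multiple imputation or inverse probability weighting for dropout, and a mixed model over baseline and five follow-up visits, from which "appropriate contrasts to test the intervention effect at specific time points (e.g., 12 months) will be constructed".

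Two further power statements rest on full enrolment. One is for an exploratory scale: "With this sample size, power is sufficient to see at least a 0.26 standard deviation (SD) difference in Generalized Self-Efficacy". The other, under Aim 2, is for the food security score in the food secure group: "80 caregivers per study arm will provide 80% power" for a 0.45 SD difference at a given time point.

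**The concern.** Enrolment exceeds the calculated number by 4 caregivers per arm, while the primary outcome is measured a year after discharge by telephone or web survey. If 236 already contained an attrition allowance, there would be no problem. If it does not, the stated 80% needs practically complete 12-month follow-up, which the SAP's own cited experience does not suggest.

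What is at stake is how a null Aim 1 result would be read. A reader told that power was 80% for a 0.36-point difference would give a non-significant result more weight than the design may support.

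**Working it through.** **Inputs** (SAP, Aim 1 sample size paragraph): difference 3.92 − 3.56 = 0.36; SDs 1.47 and 1.24; 1:1 allocation; power 0.80; alpha 0.05. Sidedness is not stated; two-sided reproduces the SAP's figure and one-sided does not (185 per arm after the adjustment). The nonparametric adjustment is taken as the Mann-Whitney asymptotic relative efficiency, 3/π.

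**Reproducing 236.**
- Variance sum: 1.47² + 1.24² = 3.6985.
- Normal approximation: 3.6985 × (1.960 + 0.842)² / 0.36² = 224.0 per arm; × π/3 = 234.6.
- t-test version: 224.95 × π/3 = 235.6, which rounds up to 236.

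The match is exact without a dropout term. Slack: 1 − 236/240 = 1.7%.

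**Power on the SAP's own basis** (arm only, caregivers with 12-month data). With n per arm:
- Power = Φ(0.36 / √(3.6985 × (π/3) / n) − 1.96)
- Detectable difference at 80% power = 2.802 × √(3.6985 × (π/3) / n)

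The retention values are assumptions: 80% and 71% are the prior-trial rates, and 90% is a more favourable case.

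| 12-month retention | n per arm | Power | Detectable difference |
|---|---|---|---|
| 100% | 240 | 80.9% | 0.356 |
| 98.3% | 236 | 80.2% | 0.359 |
| 90% | 216 | 76.7% | 0.375 |
| 80% | 192 | 71.7% | 0.398 |
| 71% | 170.4 | 66.6% | 0.422 |

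A t-based version gives 76.5%, 71.5% and 66.3% for the last three rows.

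**Credit for baseline and earlier visits.** The documents give no within-person correlation r, so 0.3, 0.5 and 0.7 are assumed.
- Baseline as covariate: the variance is multiplied by (1 − r²).
- Longitudinal: six visits, equal correlation between all visits, dropout permanent and linear by visit, Gaussian approximation to the 5-point item, contrast taken as the arm difference at 12 months.

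| Power at r = 0.3 / 0.5 / 0.7 | 90% retained | 80% retained | 71% retained |
|---|---|---|---|
| Baseline as covariate | 81 / 87 / 96% | 76 / 83 / 94% | 71 / 79 / 92% |
| Longitudinal, baseline means held equal | 81 / 88 / 97% | 76 / 84 / 95% | 72 / 81 / 93% |
| Longitudinal, baseline arm difference free | 77 / 78 / 79% | 73 / 75 / 77% | 69 / 71 / 75% |

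With baseline as covariate, the correlation that restores 80% power is √(1 − n/234.56): 0.28, 0.43 and 0.52 at 90%, 80% and 71% retention.

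**The other two figures** (two-sample t-test, 80% power).
- Generalized Self-Efficacy: n = 240 gives 0.256 SD, the stated 0.26. At 216, 192 and 170.4 it is 0.270, 0.287 and 0.304 SD. With the SAP's SD of 5, 1.3 points becomes about 1.35 to 1.5.
- Food secure group: n = 80 gives 0.446 SD, the stated 0.45. At 72, 64 and 56.8 it is 0.470, 0.499 and 0.530 SD. This matters only at late time points.

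**The case against.** The strongest reply is that the arm-only calculation was used for sizing, while the planned analysis is a mixed model on all 480 with imputation or weighting. Setting the Mann-Whitney basis against only those observed at 12 months describes a test the SAP does not plan. At 90% retention the longitudinal model gives 81% to 97% power with equal baseline means, and falls at most about 3 points short with free baseline means. This stands as a reason not to say that the trial is underpowered. It does not rescue the stated 80%. Imputation and weighting are offered against bias, and restore precision only as far as other data predict the missing value. The SAP lists baseline among the time points of the time-by-arm interaction and adds covariates only after serious imbalance. If that leaves the baseline arm difference free, power stays below 80% in every case examined with 10% loss or more.

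The retention rates are also open to challenge. They come from another trial, are not at 12 months, and 71% is joint completion of three surveys, so single-visit retention may be higher. The planned monthly contacts may help. All of this is fair, and the shortfall figures are conditional on it. Even so, 90% retention gives only 77% on the stated basis.

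It is also right that 1.7% is only where power crosses 80%. The decline is gradual: about 79% at 5% loss.

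Last, Generalized Self-Efficacy is exploratory and its change is small. It and the food secure figure are included only because they share the same zero-loss basis.

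**Conclusion.** The concern holds. The 236 is the number analysed, enrolment adds 1.7%, and neither document states a 12-month retention or inflates for loss. On the SAP's own basis the stated 80% power becomes 77%, 72% or 67% at an assumed 90%, 80% or 71% retention. Under the longitudinal model it could lie anywhere from about 69% to 97% over the same retention range and assumed correlations of 0.3 to 0.7, depending mainly on whether baseline arm means are held equal. The documents do not settle retention, correlation or baseline handling, so a reader cannot tell whether true power is below or above 80%. The computed 236 is itself correct; what is wrong is presenting 80% power as what enrolling 480 delivers at 12 months.

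**What to change.** In the Aim 1 sample size paragraph, state an expected 12-month retention and its source. Then restate power for 0.36 points, and the detectable difference, over a range such as 71% to 90%, on one named basis:

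1. the existing arm-only basis, which gives 67% to 77% power and 0.42 to 0.38 points; or
2. the planned longitudinal model, saying whether baseline self-efficacy is a covariate or baseline arm means are held equal, and giving a range for the within-person correlation.

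Restate the 0.26 SD figure in the same way and, for late time points, the 0.45 SD figure.

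This is SAP wording only, with no added enrolment. The price is a less favourable stated power under option 1, or an explicit correlation assumption under option 2. It makes the power statement accurate but does not raise the power. For scale, keeping 236 per arm with 12-month data would take 236/0.90 = 263 per arm (526 in total) at 10% loss, or 236/0.80 = 295 (590) at 20% loss.

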point Likert scale ranging from “not at all confident” to “completely confident.” The pragmatic CRx intervention was delivered to an adult patient by a patient service representative or ER nurse at the time of discharge from an ambulatory care visit with no specific counseling. The CRx-H iteration is more intensive (e.g. initiated in the hospital by a navigator, ongoing support via text messaging). We therefore hypothesize that CRx-H may also promote General Self-Efficacy (a broader concept than self-care self-efficacy) and will explore this by administering the Generalized Self-Efficacy Scale (range 10-40) at baseline and at follow-up.

Secondary outcomes will also be measured longitudinally. Caregiver health will be assessed using the Medical Outcomes Study Short Form-12 (the CRx trial saw positive trends in the physical component score at 3 months). Caregiver-reported child health will be assessed with a widely used, well-validated single-item physical and mental health measure from the National Survey of Child Health. Recognizing significant limitations of self-reported nutrition assessment, we will estimate caregiver nutrition using the 2-item CUP Fruit and Vegetable Screener (FVS), and will adapt this item to elicit caregiver-reported child nutrition. Child healthcare utilization, including time to child follow-up for the post-discharge medical visit, time to and number of ER visits, and time to and total days of hospitalization will be obtained from the child’s EMR and caregiver self-report.

Analysis and Sample Size Justification: To determine the impact of the CRx-H intervention on the highest-risk group, Aim 1 analyses will focus on 480 food insecure caregivers. Descriptive statistics will be used to summarize, overall and by study arm, sociodemographic characteristics and primary and secondary outcomes at each measured time point. The mean, standard deviation, median, and inter-quartile range will be generated for continuous variables; frequency counts and percentages will be generated for categorical variables.

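### The 80% power for the Aim 1 primary outcome is not supported by the SAP's own means and SDs: smooth 5-level distributions that match them give the named ordinal test about 67-68% at 236-240 per arm

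*SAP*

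**What the plan says.** SAP, Aim 1, sample size justification: "For the primary outcome (self-efficacy for self-care at 12 months) a sample of 236 caregivers per arm" is said to detect a difference like that in the earlier CRx trial, given as "3.56 +/- 1.47 vs. 3.92 +/- 1.24". The calculation was made "with nonparametric adjustment accounting for the fact that an ordinal logistic model" containing only the study arm corresponds to a rank-sum (Mann-Whitney) test. Its settings were "sample size calculation using a group allocation of 1:1; power=0.8", and alpha was 0.05. Enrolment is then set at 480 food insecure caregivers, or 240 per arm.

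The measure is one confidence question on a 5-"point Likert scale ranging from" no confidence to complete confidence, and the SAP says the CRx trial used the same measure. The Aim 1 analysis section lists self-efficacy among the ordinal outcomes and plans a longitudinal mixed model with a 12-month contrast. The SAP gives no size for the nonparametric adjustment, no sidedness for alpha, and no category frequencies for the item.

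**The concern.** The SAP ties its 80% to a rank or ordinal test of a 5-level item with four stated moments. A normal-theory efficiency factor answers a different question: how a rank test performs on continuous normal data with equal spread. Here the scale has a ceiling, and the arm with the higher mean also has the smaller SD. If the named test has materially less power under the SAP's own inputs, a true effect of the planned size would be missed more often than the one time in five that the SAP accepts. This concerns the primary outcome, and the calculation makes no allowance for loss to follow-up.

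**Working it through.** **Inputs (SAP, Aim 1).** Means 3.56 and 3.92; SDs 1.47 and 1.24; levels taken as 1 to 5; allocation 1:1; alpha 0.05, taken as two-sided; power 0.80.

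**Step 1: reproduce 236.**
- Difference = 3.92 - 3.56 = 0.36. Common SD = sqrt((1.47² + 1.24²)/2) = 1.360. Standardised difference d = 0.36/1.360 = 0.265.
- Normal formula: n = 2(1.960 + 0.842)²/d² = 224 per arm. The noncentral t gives 225.
- 225/(3/pi) = 225/0.955 = 235.6, i.e. 236.
- Alternatives tried: no adjustment 224-225; minimum efficiency 0.864, 259-260; logistic-parent efficiency, 204; one-sided with 3/pi, 185. None fits. Noether's formula for normal data gives 237, on the same normal assumption.

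**Step 2: put the same moments on five levels.** The maximum-entropy distributions with exactly the stated means and SDs are:

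| Level | 1 | 2 | 3 | 4 | 5 |
|---|---|---|---|---|---|
| Control | 0.148 | 0.124 | 0.137 | 0.201 | 0.389 |
| CRx-H | 0.064 | 0.094 | 0.148 | 0.248 | 0.447 |

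- P(Y > X) + 0.5 P(tie) = 0.428 + 0.5 × 0.265 = 0.561.
- Tie-corrected null standard error = sqrt[(1 - Σt³)/12 × 2/n], where t is the average share at each level. With 1 - Σt³ = 0.910 and n = 236, this is 0.02535.
- Power = Φ(0.0610/0.02535 - 1.960) = 0.672. Using the variance under the alternative gives 0.673. At 240 per arm it is 0.680.

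**Step 3: other shapes and methods, all with the same four moments.**
- Tie-corrected Mann-Whitney at 236 per arm: beta-binomial 0.677; cut latent normal 0.681.
- Whitehead's ordinal formula, three shapes: 0.676-0.684.
- Simulation of 20,000 trials, maximum entropy: 0.670. A t-test on such data has about 0.82.
- At 240 per arm, the three shapes give 0.680-0.688. About 314-319 per arm would be needed for 0.80.

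**Step 4: where the loss comes from.** Shift the Step 2 control distribution by proportional odds to a mean of 3.92. The odds ratio is 1.61 and the intervention shares become 0.097, 0.091, 0.113, 0.192, 0.507. Power at 236 is 0.806, on an item just as coarse, so ties are not the cause. The intervention SD, however, is then 1.36, not 1.24. The two cases compare as follows:

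| Change from control | Share at levels 1-2 | Share at level 5 |
|---|---|---|
| All four SAP moments | 0.272 to 0.158 (-0.114) | 0.389 to 0.447 (+0.058) |
| Proportional odds | 0.272 to 0.188 (-0.084) | 0.389 to 0.507 (+0.118) |

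The mean gain is 0.36 in both. With the SAP's SDs, more of it comes from fewer low scores, which ranks weigh less than means do.

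**Step 5: range.** Among random 5-level pairs matching all four moments, power at 236 has median 0.69 and a 5th-95th percentile range of about 0.39-0.85; about 15% reach 0.80, and the extremes are about 0.09 and 0.96. Restricting to regularly rising category shares gives 0.58-0.81, median 0.72.

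**The case against.** The strongest reply is that four moments do not determine rank-test power, so 67% reflects a chosen shape. That stands: the ranges in Step 5 include 0.80, and the figure needs its assumption beside it. But three smooth shapes agree, and most matching pairs fall short.

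Second, the SAP plans for a difference only similar to that in the CRx trial, and SDs from that trial are estimates. The same means with SDs 1.42 and 1.30 give 0.82 by the method of Step 2, and equal SDs of 1.36 give about 0.91-0.92. This also stands as a reason for a sensitivity range. It does not rescue the calculation as printed, because the SAP states 1.47 and 1.24. Nor does proportional odds, the usual assumption of the ordinal model: it returns about 0.81 only by replacing the printed intervention SD, and a search found no proportional-odds pair matching all four moments.

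Third, the planned analysis is a longitudinal mixed model with baseline and repeated measures, not a two-group test. Its power could be higher or lower. The SAP gives no correlations from which to compute it, and it based its own sample size on the two-group test.

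A reader might infer that the SAP made an arithmetic slip, or that any 5-level item with many ties loses this much power. Neither is supported: 236 is reproducible, and Step 4 shows the same item reaching 0.80 under a different pattern of change.

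**Conclusion.** Wrong as written: the stated 80% is not supported by the SAP's own inputs for the test it names. For smooth 5-level distributions with the stated means and SDs, the unadjusted two-group rank or ordinal test has about 67-68% power at 236-240 per arm. Under those shapes a true effect of the planned size would be missed about one time in three.

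This rests on three assumptions: a two-sided alpha, response shapes that the documents do not give, and a test without baseline or repeated measures. That the adjustment was 3/pi is inferred from the match to 236. It would go too far to say that the trial's power is 67%. The CRx frequencies could put it above or below that, and some admissible shapes reach 0.80.

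**What to change.** Recompute the power for 240 per arm from the CRx trial's category frequencies by arm for this item, using a tie-corrected Mann-Whitney formula, Whitehead's ordinal formula or simulation. State the method and the sidedness of alpha. Restate the power for 480 with a sensitivity range over plausible response distributions, including the proportional-odds case and somewhat closer SDs, in place of the 80% from the normal-data adjustment.

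No participants need be added. The primary ordinal contrast should not be changed to a difference in means merely because that looks better powered. The cost is a short recalculation and probably a less favourable stated power. Since the CRx trial used the same item, the frequencies should be recoverable.
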